## LIST OF ABBREVIATIONS

Abbreviation	Definition
(e)CRF	(electronic) Case Report Form
ADE	Adverse Device Effect
AE	Adverse Event
AESI	Adverse Event of Special Interest
APR	Annual Progress Report
AR	Adverse Reaction
ASADE	Anticipated Serious Adverse Device Effect
BCVA	Best-corrected visual acuity
CA	Competent Authority
CI	Coordinating Investigator
CIP	Clinical Investigation Plan
CM	Concomitant Medication
CRA	Clinical Research Associate
CRF	Case Report Form
DD	Device Deficiency
DMC	Data Monitoring Committee
EC	Ethics Committee
ECG	Electrocardiogram
EMR	Electronical Medical Record
FAMHP	Federal Agency for Medicines and Health Products
FPFV	First Patient First Visit
GCP	Good Clinical Practice (latest version of ICH E6)
GP	General Practitioner
IB	Investigator Brochure
ICF	Informed Consent Form
IMD	Investigational Medicinal Device
ISF	Investigator Site File
KWS	Klinisch workstation, i.e. the EMR used in the UZ Leuven
Log MAR	Logarithm of the minimal angle of resolution
LPLV	Last Patient Last Visit
PI	Principal Investigator (Participating Site)
PRO	Patient Reported Outcome
SADE	Serious Adverse Device Effect

SAE	Serious Adverse Event
SAR	Serious Adverse Reaction
TMF	Trial Master File
USADE	Unanticipated Serious Adverse Device Effect

---

## FUNDING AND SUPPORT

---

Funder	Type of Financial or Non-Financial Support
Carl Zeiss Meditec AG	Grant

---

## ROLES AND RESPONSIBILITIES

---

The Principle Investigator (PI) is responsible for the conduct of the Investigation at his/her Participating Site, and for protecting the rights, safety and well-being of the participants. As such the PI must ensure adequate supervision of the Investigation conduct at the Participating Site. If any tasks are delegated, the PI will maintain a log of appropriately qualified persons to whom he/she has delegated specified Investigation-related duties. The PI will ensure that adequate training is provided and documented for all Investigation staff, prior to conducting assigned Investigation-related activities.

It is the Coordinating Investigator's (CI's) responsibility to supervise the general conduct (e.g., study progress, communication, CIP training and support of the participating sites, annual reporting, end of Investigation notification(s) and results reporting etc.) of the Investigation. The CI fulfils both Investigator's and Sponsor's responsibilities, as outlined in ISO 14155:2020 and applicable regulations.

PI and CI shall each be referred to as «Investigator(s)».

## CIP SYNOPSIS

Title of clinical Investigation («Investigation»)	Title: ZEISS RESIGHT Disposable Lenses evaluation study
CIP Short Title Acronym	RESIGHT Disposable
Sponsor name	<University Hospitals Leuven (UZ Leuven) or KU Leuven>
Coordinating Investigator	[name]
Contact Address CI	UZ Leuven, [name]
Contact Email CI	[contact]
Contact Phone CI	[contact]
SIN number	CIV-23-02-042213
Other public database number	not applicable
Principal Investigators and Participating Sites	not applicable
Medical condition or disease under investigation	-Macular pathology requiring surgery: macular pucker, macular hole, vitreomacular traction -Retinal detachment
Study rationale	See row below
Primary objective	To evaluate the intra-operative efficacy of a new intra-operative viewing device.
Secondary objective(s)	/
Clinical Investigation Design	Investigator-initiated, mono-center, academic, prospective, interventional case study
Endpoints	To determine the effectiveness of the device compared to the reusable RESIGHT lenses and Vitreq contact lens presently used as standard-of-care.
Sample Size	120 eyes in two cohorts (60 in each cohort)
IMD	Disposable RESIGHT lenses
Comparator device(s)	Reusable RESIGHT lenses and Vitreq contact lens
Maximum duration of treatment of a Participant	Total inclusion time of each patient is surgery time (from first incision till removal of vitrectomy cannulas)
Maximum duration of the Investigation	Total inclusion time of each patient is surgery time (from first incision till removal of vitrectomy cannulas)
Anticipate First Patient First Visit (FPFV)	Q1 2023
Anticipate Last Patient Last Visit (LPLV)	Q4 2023
Third Parties	Carl Zeiss Meditec AG, [name]; Grant

## STUDY FLOWCHART

### Schedule of Events – Study specific Procedures / Assessments

[figure not shown]
**i** Please indicate in the flowchart with different colors whether a procedure is performed as part of the **standard of care** or **specifically for the Investigation**. Describe the visits and applicable procedures/investigations (with a reference number or letter) in more detail in a footnote below the study flowchart

Procedures/ Assessment	Pre-surgery	Surgery
Timing (weeks)	0	0
Informed consent	X 	
Inclusion / Exclusion criteria	X	
Randomisation	X	
Vitrectomy +/- Phaco parameters		X
Device Deficiencies		X
(Serious) Adverse event (S)(AE) assessment		X

*1 : Informed Consent process should take place prior to all other study-related procedures at the screening visit*

## I Background and Rationale

For several eye disorders, a surgical therapy is required. Depending on the type of surgery, different areas of the eye need to be visualized. For this purpose, a dedicated ophthalmic microscope is used. To view the anterior segment (i.e. the lens and all structures anterior to it), no additional optical attachment is required. To visualize the posterior segment (i.e. all structures posterior from the lens), an additional optical system is required in conjunction with the surgical microscope.

## 1.1 Surgical microscope device

For this purpose, a modern ophthalmic surgical microscope such as the ARTEVO 800 used in our center, integrates many functions.

### 1.1.1 Double binocular optical tract.

*The ARTEVO 800 digital 3D microscope system.*

*Left: the microscope mounted on its floor stand, with touchscreen control pane on the microscope arm. Right: the 55" 3D visualization screen.*

Since stereopsis is required during surgery, both the main viewer and the assistant viewer have a binocular optical tract.

### 1.1.2 Red reflex

During cataract surgery, it is required to visualize both the front and rear side of the lens. For this purpose, a co-axial light source is built in the microscope, which generates a red reflex by reflection from the retina in the back of the eye. The balance between red reflex light and environmental light can be controlled by surgeon.

### 1.1.3 Wide-angle retina viewing system

During posterior segment surgery (vitrectomy), viewing of the retina is required. For that purpose, an

additional optical system below the microscope is required.

These optical systems can be divided into two categories:

1) Contact lens systems

[figure not shown]
This lens type is placed on the corneal surface with some contact gel in between the cornea and the lens. Different lenses are being used, either with a convex surface for wide-angle viewing or with a flat (or concave) surface for high-magnification viewing. In the former lens type, an image inverter is required to generate an erect retina image for the surgeon.

Although the optical quality of these contact lenses is very good, there are several disadvantages:

- The continuous contact with the corneal surface may cause corneal lesions (epithelial defect), or cause corneal edema during prolonged surgery sometimes rendering retinal visualization impossible necessitating to discontinue the surgery.
- The lens must be kept in a horizontal position on the eye, which requires an experienced surgical assistant to stabilize the lens during surgery. In our center, the surgical assistance is performed by residents in training who rotate every 6 weeks. Hence, it is impossible to have a well-trained surgical assistant for this purpose.
- When using a wide-angle viewing lens, although an extreme wide-field angle can be obtained, this field-of view is highly limited by the pupil size. Since vitrectomy surgery is usually performed in patients >65 years of age, the pupil dilation is often limited, restricting the field-of view.

As a result, the use of a contact lens during vitrectomy surgery is only occasionally used during surgery.

[figure not shown]

Specifically for the Zeiss microscopes, the RESIGHT system can be used. This device is mounted below the microscope, and allows the surgeon to look through a lens which is held by a swing arm just above the surface of the eye. The RESIGHT system is highly integrated within the ZEISS LUMERA/ARTEVO microscopes, which has several ergonomical advantages. Firstly, the microscope automatically changes several settings (illumination, foot pedal control, inverting system, ...) when the RESIGHT is inserted into the field-of-view. Secondly, the focusing can be done with the microscope foot pedal and the system focuses internally whereby the distance between the surgical lens and the cornea remains unchanged.

Since the purchase of our LUMERA 700 (and later on: ARTEVO 800) microscopes, we have been using the RESIGHT system for all our vitrectomy surgeries.

The RESIGHT provides two selectable lenses, the 60D (green one) and the 128D (yellow one).

The yellow lens has lower magnification and more overview to allow good visualization of the periphery. The green lens provides higher magnification for macular surgery but as a consequence offers less overview in the eye. During vitrectomy for macular surgery, the lenses will be switched a few times by dialing the

desired lens in front of the eye. During the vitreous removal and the lasering of the retina, the yellow lens is used. During the macular surgery (e.g. removal of epiretinal membrane or peeling of the inner limiting membrane), the green lens is used.

At present, both RESIGHT lenses are reusable and are cleaned and sterilized (reprocessed) together with the RESIGHT system itself after every surgery. These reusable lenses are validated for 200 reprocessing cycles. We do notice that after a few dozen reprocessing cycles, wear & tear occurs which results in the following observations:

- The lens surface shows scratches from the cleaning process, which deteriorates the surgeons' view.
- The lens surface shows stains, created by leftovers of the cleaning agents used. These stains become permanently “baked” into the lens surface due to the heat from the sterilization process.
- Condensation occurs on the lower surface of the lens (closest to the eye surface), again hindering the surgeon's view.

Picture of RESIGHT wide angle viewing system mounted underneath the ARTEVO microscope.

#### 1.1.4 3D Viewing

[figure not shown]
The ARTEVO 800 microscope head has two high-resolution (4K) cameras built-in, that allow the projection of a 3D image on a 55 inch screen. The surgeon can choose to perform the surgery using the screen while wearing (passive) 3D glasses. In this surgical mode, the surgeon is not looking through the microscope, but directly on the 3D screen to perform the surgery. However, for surgeons who prefer not to work on the 3D screen, the microscope can be switched to “hybrid” mode where the surgeon looks through the ocular of the microscope while the other people attending the surgery can view the image on the 3D screen. Even in the middle of a procedure, the surgeon can choose to switch between 3D and hybrid mode by simply flipping a button on the microscope. Because of the high sensitivity of the 4K cameras, less light is required compared to traditional oculars. Mainly during retina surgery using endo-illumination, this makes the surgery safer by reducing the incidence of light-toxicity to the retina. Moreover, a smaller numerical aperture (‘diaphragm’) can be used for 3D visualization, which increases the depth-of-field compared to viewing through an ocular.

However, a side-effect of the increased depth-of-field is that scratches / stains / condensation on the

RESIGHT lens surface will be more visible. Hence, a clean optical pathway is mandatory for adequate visualization in 3D surgery.

### 1.1.5 Image layover

[figure not shown]
During cataract surgery, a pre-operative photo of the eye (taken with the ZEISS IOLMASTER biometer) can be uploaded in the ARTEVO 800 microscope. Using an image recognition algorithm, the microscope can project additional information on the surgical image. This augmented reality system can show the surgeon the exact incision sites, the correct placement of the capsulorhexis (i.e. the opening that the surgeon makes in the front capsule of the lens), the axis of alignment of a toric implant lens that needs to be rotated in a correct angle in the eye etc.

*CALLISTO augmented reality: a live projection of the horizontal axis (yellow) and required positioning of a toric implant lens (blue) is available in overlay on the surgical image.*

### 1.1.6 iOCT

Optical Coherence Tomography (OCT) was first introduced in ophthalmology in the mid-nineties for retinal viewing. Since then, the use of OCT has expanded extensively, and has now become one of the main technologies used for eye imaging, both in the anterior and the posterior segment. This OCT technology is now also available integrated in surgical microscopes (iOCT), and offers real-time visualization of the cornea, the lens and the retina.

## 1.2 Disposable RESIGHT Lenses

These wear & tear disadvantages can be overcome by using disposable lenses mounted on the RESIGHT system. Such disposable lens system compatible with the RESIGHT is already available from a third-party source (Oculus LenZ), but is not implemented in our center because of the high cost. Moreover, this Oculus LenZ is shaped to replace both the high-magnification 60D RESIGHT lens (green) and the wide-field 128D RESIGHT lens (yellow), but this does not offer the same optical quality compared to each of these two separate lenses.

ZEISS has designed a series of disposable lenses that are compatible with the RESIGHT system.

1. WIDE-ANGLE LENS (Yellow)
2. MACULA LENS (Green)
3. ULTRA WIDE-ANGLE LENS (Purple)

All three lenses are created from the same material:

- Optical part: PMMA (poly-methyl methacrylate = "plexiglas")
- Holder arm: ABS20 (acrylonitrile butadiene styrene; same material as Lego bricks)
  - MACULA LENS: color green 509
  - WIDE-ANGLE LENS: color yellow 408
  - ULTRA WIDE-ANGLE LENS: color traffic purple 854

These materials are commonly used for medical applications and can be sterilized in ethylene-oxide without deformation, opacification or leaching.

I had the opportunity to test these prototypes of these lenses on *in vivo* pig eyes in lab conditions. From these preliminary tests, the following conclusions were drawn:

1. The disposable wide-angle lens has the same use as the present reusable yellow lens, but its improved design makes it possible to use this lens for both peripheral work as well as macula surgery.
2. Macula lens: this lens has the same macula surgical use as the present reusable green lens. However, its improved resolution provides comparable or even better performance than a flat contact lens.
3. Ultra-Wide angle lens: this newly designed lens provides the same wide-angle view as a convex contact lens, albeit without any contact with the corneal surface. However, this ultra-wide lens must be kept closer to the corneal surface compared to the yellow lens, hence may condensate more easily.

Apart from the optical improvements, the use of disposable RESIGHT lenses is expected to also overcome the issues that we presently encounter when using the reusable lenses:

- No scratches or stains on the lens surface since a brand-new lens is used in every surgery.
- Not more (or minimum) condensation of the lens surface of the disposable lens as compared to the reusable lens since each disposable lens will have an intact coating.

## 2 Objectives and Design

### 2.1 Study objectives and hypotheses

This study is designed to obtain more information on the efficacy of the disposable RESIGHT lenses in routine vitrectomy surgery. This information can lead to adjustments to these surgical lenses to further fine tune a device which can be used by other surgeons.

[figure not shown]
Theoretically, both the improved lens design and better resistance to fogging should improve the visualization of the retina hence facilitate the surgery, increasing the surgical safety.

During the surgery, a comparison will be done between the present lenses used (reusable RESIGHT lenses and disposable Vitreq contact lens) and the new disposable RESIGHT lenses. For that purpose, both lenses will be mounted on the rotating arm of the RESIGHT allowing the surgeon to toggle between both lenses during surgery. This toggling takes a few seconds, hence the total surgery time may be extended by ~30 seconds. However, this will most likely not impact patient safety since a vitrectomy surgery typically requires one hour time.

To compare the image generated by the present and the new RESIGHT lenses, both still shots and (short) video recordings will be created during the surgery. For this purpose, the internal camera and recording system of the ARTEVO microscope will be used. This will not have any impact on the surgery duration. Since only the retinal image is recorded, there is no risk of patient recognition on the recorded photos and videos.

Moreover, the Artevo microscope has a function that generates anonymous data export which will protect the patients' identity.

Although there is no contact between the lens and the patient, the lens is touched by the surgeons' glove, hence must be sterile. ZEISS will deliver these lenses pre-sterilized according to the present required standards. ZEISS will provide these lenses packaged and labeled according to their specifications.

## 2.2 Primary Endpoints

The purpose of this study is to evaluate the intra-operative efficacy of new intra-operative viewing device, more specifically:

[figure not shown]
1. To determine whether the performance of the disposable MACULA LENS is comparable or even better than a flat contact lens, due to its improved resolution. For this purpose, the in-house available Vitreq contact lens will be used.  
This parameter will be determined in the macular surgery study arm only.
2. To determine that the disposable ULTRA WIDE-ANGLE LENS does not condensate / condensates to a lesser extent during surgery.  
This parameter will be determined in both study arms.
3. To determine that the disposable ULTRA WIDE-ANGLE LENS allows for imaging up to ora serrata on human eyes, reducing the need for indenting. This parameter will be determined in the retinal detachment surgery study arm only.
4. To evaluate whether both peripheral vitrectomy as well as macula work are possible with the disposable wide-angle lens. This parameter will be determined in the macular surgery study arm only.
5. To evaluate the amount of fogging that occurs when using the disposable wide-angle lens compared to using the reusable yellow lens.
6. To evaluate whether the amount of light to illuminate the retina is reduced when using any of the disposable lenses compared to the reusable yellow/green lenses. This parameter will be

determined in both study arms.

7. To evaluate whether the disposable lenses show a more natural color representation compared to the reusable yellow and green lenses. This parameter will be determined in both study arms.
8. To evaluate whether the iOCT quality recorded with the disposable macula lens is similar to or better than the iOCT recorded using the green reusable lens. This parameter will be determined in the macular surgery study arm only, where iOCT is being recorded as standard-of-care.

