## 7 Statistics and Data Analysis

Statistical analysis will be performed in accordance with ICH E9; a detailed description of the analysis is provided in the study-specific Statistical Analysis Plan (SAP). ICH E3 and E8 will guide the structure and content of the clinical study report.

The statistical analysis for the clinical investigation will be outsourced to a licensed medical statistician (Ars Statistica).

A pseudonymized Excel-export will be generated from the eCRF for statistical analysis.

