### 7.2 Statistical Analysis

#### 7.2.1 Efficacy Analysis

All endpoints: For group comparisons, continuous data will be compared by means of T-test/ANOVA when homogeneity of variances, tested with the Bartlett's test, and normality of the residuals, tested with the Shapiro-Wilks test, will be reached and means and standard deviations (means  $\pm$  StDev) will be reported. When homogeneity of the variance or normality of the residuals will not be proved, Wilcoxon signed rank/Kruskal-Wallis test will be performed on rank data and medians and inter-quartile ranges (median [Q25 – Q75]) will be reported. Next, the dependence between two continuous variables will be studied through Pearson's correlation. Last, for count data, the Pearson Chi-Squared test will be performed to compare proportions.

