#### 7.2.2 The level of statistical significance

The statistical significance level will be 5%

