#### 7.2.4 Procedures for reporting any deviations from the original statistical plan

The final statistical plan will be agreed prior to final data lock and prior to any analyses taking place. Any deviation thereafter will be reported in the final trial report.

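### Primary endpoints 1 and 8 ask whether a lens is comparable or similar, but section 7.2.1 provides only difference tests and a correlation, with no margin or confidence-interval rule

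*Combined protocol and SAP*

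**What the plan says.** Section 2.2 lists eight primary endpoints. Endpoint 1 asks whether the "performance of the disposable MACULA LENS is comparable or even better than a flat contact lens", with the Vitreq contact lens as comparator. Endpoint 8 asks whether iOCT quality with the disposable macula lens "is similar to or better than the iOCT recorded using the green reusable lens". Both are assessed in the macular surgery arm only, which has 60 eyes (section 2.3).

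Section 7.2.1 sets one analysis for everything: "All endpoints: For group comparisons, continuous data will be compared by means of T-test/ANOVA" if variance and normality checks are passed, and Wilcoxon signed rank or Kruskal-Wallis tests otherwise. It adds Pearson's correlation for pairs of continuous variables and ends: "Last, for count data, the Pearson Chi-Squared test will be performed to compare proportions". Results are summarised as mean ± SD or median with quartiles. Section 7.2.2 adds "The statistical significance level will be 5" per cent, without saying one- or two-sided. Section 7.1 gives only the number of eyes and cohorts.

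Section 7 refers to a study-specific SAP for the detail. Section 7.2.4 states: "The final statistical plan will be agreed prior to final data lock and prior to any analyses taking place".

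**The concern.** An endpoint that is met when the new lens is either as good or better is a non-inferiority question. Answering it requires a statement of how large a deficit would still count as comparable, and an analysis that can exclude a deficit of that size. Section 7.2.1 contains neither. Its tests take no difference as the null hypothesis. Rejection in favour of the new lens supports *better*; failure to reject supports nothing in particular.

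For two of the eight primary endpoints, the more modest of the two permitted conclusions therefore has no valid route in the stated analysis. A non-significant result would not distinguish a real match from data too imprecise to reveal a deficit.

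Timing matters as well. Under section 2.3 the surgeon records the parameters after each operation. Section 7.2.4 requires the final plan before data lock and before analysis, which still allows a margin to be chosen after every eye has been rated.

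**Working it through.** **The plan's own figure.** Section 7.1 gives 120 eyes in two cohorts with no power, effect size, SD, rate or margin, so it cannot be reproduced. The calculations below are illustrations.

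**Inputs**
- From the documents: n = 60 macular eyes (section 2.3); 5% level (section 7.2.2), taken as two-sided.
- Assumed: 60 complete pairs. For endpoint 8, section 2.1 offers support, since "both lenses will be mounted on the rotating arm of the RESIGHT" and the surgeon toggles between them, although it does not say that iOCT is recorded through both lenses in every eye. For endpoint 1 pairing is purely an assumption: the contact lens sits on the cornea (section 1.1.3), and nothing says both lenses are rated in every macular eye.
- Assumed: true deficits, adequacy rates, within-eye correlation 0 to 0.3, and margins.

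**1. Difference test on a score.** Paired t-test, 59 df, critical value 2.001. For a true deficit of d SDs of the paired differences, the noncentrality is d√60. At d = 0.25 this is 0.25 × 7.746 = 1.936; power is 47.8%, so p>0.05 in 52.2% of trials. The result depends strongly on d:

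| True deficit (SD) | P(p>0.05) |
|---|---|
| 0.20 | 67% |
| 0.25 | 52% |
| 0.30 | 37% |
| 0.40 | 14% |
| 0.50 | 3% |

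The 95% CI half-width is 2.001/√60 ≈ 0.26 SD.

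**2. Difference test on a proportion.** Suppose 85% of views are adequate with the disposable lens and 95% with the comparator. If exactly 51/60 and 57/60 were observed, the pooled rate is 0.90, the SE is √(2 × 0.90 × 0.10/60) = 0.0548, and z = 0.10/0.0548 = 1.83. Chi-squared is then 3.33, below the critical 3.84. Over repeated trials, Pearson chi-squared gives p>0.05 in 54–55% across correlations 0 to 0.3.

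**3. A margin rule on the same deficits.** Comparability is concluded if the lower 95% limit lies above minus the margin.
- Score, margin 0.37 SD: noncentrality (0.37 − 0.25)√60 = 0.93, so the 0.25 SD deficit is called comparable in 14.8% of trials. With no true difference, noncentrality is 0.37√60 = 2.87 and power is 80.5%.
- Proportion (Tango paired score test, one-sided 2.5%, exact enumeration), 85% against 95%: called comparable in about 2% with a 10-point margin and 13–14% with a 15-point margin. The 2% is simply the error rate, because that margin equals the assumed deficit.

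**4. Power of the margin rule when the lenses are truly identical** (range over correlation 0 to 0.3):

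| True adequacy | 10-point margin | 15-point margin |
|---|---|---|
| 95% | 59–70% | 89–95% |
| 90% | 38–50% | 73–83% |
| 85% | 31–39% | 60–73% |

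**5. If the form holds one worse/same/better rating per eye.** Take 80% same-or-better as an example minimum. The Clopper-Pearson lower limit is 79.5% for 54/60 and 81.6% for 55/60, so 55 are needed. The chance of reaching 55 is 92% if the true share is 95%, and 44% if it is 90%.

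**The case against.** The strongest reply is that much of the relevant material lies elsewhere. The study-specific SAP may contain a margin, and the surgeon form and eCRF, whose content is not shown, define the scales. This stands, and it limits the finding to section 7.2.1.

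A second reply is that the plan never uses the term non-inferiority. This is an unrandomised case study meant to gather information that may lead to lens adjustments, so *comparable* could be meant descriptively. That reading is possible. However, the items are labelled primary, a significance level is set and publication is intended; and a descriptive reading still needs estimates with intervals, which section 7.2.1 does not promise.

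Third, no passage says that p>0.05 will be read as comparable, so the 52% and 54–55% are error rates of a rule the plan does not contain. This is correct. They show what would follow if the stated tests were asked to carry the conclusion, and they move a great deal with the assumed deficit. The 0.37 SD margin is only what 60 pairs support at about 80% power; it has no clinical basis.

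Fourth, readers could build rough intervals from the reported summaries. For proportions treated as unpaired they could. For paired scores they could not, because the SD of the differences is not among the listed summaries. In neither case would they have a threshold.

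**Conclusion.** The concern holds and should be fixed. As written, section 7.2.1 can establish *better* for endpoints 1 and 8 but has no criterion for *comparable* or *similar*. That conclusion follows from the text and needs none of the assumed inputs. Its practical size does depend on them: at 60 pairs, deficits of 0.20 to 0.30 SD would go undetected in 67% to 37% of trials, and a 10-point deficit from 95% in 54–55%. Whether the trial as a whole lacks a criterion cannot be settled without the separate SAP.

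**What to change.** Add to section 7.2.1 wording such as:

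> For endpoints 1 and 8 the difference (disposable minus comparator) is reported with a 95% CI, paired where both lenses are rated in the same eye. Comparability or similarity is concluded only if the CI excludes a deficit of [margin], fixed before any ratings are seen; superiority is read from the same CI. If no margin is fixed, the estimate and CI are reported and neither conclusion is drawn from p>0.05. If the form holds a single worse/same/better rating per eye, the proportion rated same or better is reported with an exact 95% CI against a pre-set minimum.

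If the study-specific SAP already contains such a rule, section 7.2.1 should cite it.

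The cost is a short text change and one decision on a margin or minimum, with no additional eyes. The price is limited power, which the plan should state. Under the assumptions above, a 10-point margin would fail truly identical lenses in 30–69% of trials, and a score needs a margin of about 0.37 SD for 80% power. Fewer than 60 pairs for endpoint 1 would lower its power further. The descriptive fallback is available if no margin that the trial can support is acceptable.

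### Primary endpoint 2 names no reference lens for less fogging and joins that comparison to an absolute no-fogging claim, so it has no single success criterion

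*Combined protocol and SAP*

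**What the plan says.** Section 2.2 lists eight primary endpoints. The second is to determine that the disposable ultra wide-angle lens "does not condensate / condensates to a lesser extent during surgery", and it is to be determined in both study arms. No reference lens follows.

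The other fogging endpoint, number 5, does name one: "To evaluate the amount of fogging that occurs when using the disposable wide-angle lens compared to using the reusable yellow lens".

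Study-level comparators appear in the synopsis ("reusable RESIGHT lenses and Vitreq contact lens") and in section 2.1: "a comparison will be done between the present lenses used (reusable RESIGHT lenses and disposable Vitreq contact lens) and the new disposable RESIGHT lenses".

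Three statements bear on the expected direction:

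- Section 1.2, on this lens in particular: "this ultra-wide lens must be kept closer to the corneal surface compared to the yellow lens, hence may condensate more easily".
- Section 1.2, in the list of what is expected of the disposable lenses as a group: "Not more (or minimum) condensation of the lens surface of the disposable lens as compared to the reusable lens".
- Section 2.1, on the disposable lenses in general: "both the improved lens design and better resistance to fogging should improve the visualization of the retina".

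Section 7.1 gives 120 eyes in two cohorts, with no fogging rate, effect size, power or margin. Section 7.2.2 sets a 5% significance level.

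**The concern.** The slash joins two different questions. That the lens does not fog is a statement about one lens. That it fogs to a lesser extent is a statement about two lenses, and the second lens is missing. The endpoint does not say whether either half suffices or which half decides.

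This affects conduct as well as reporting. The design relies on the surgeon toggling between two mounted lenses in the same eye. If the reference for endpoint 2 is not fixed before surgery, it may not be mounted and graded in that eye, and the paired observation cannot be recovered later.

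The direction is also unsettled. Section 1.2 gives a specific caution that this lens may fog more easily and a group expectation of no more fogging, while the endpoint claims less. No more is a non-inferiority claim and needs a margin. Less is a superiority claim. A result could satisfy one and miss the other.

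**Working it through.** **Step 1. Is the missing reference only a matter of style?** Set the endpoints of section 2.2 side by side:

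| Endpoint | Reference named |
|---|---|
| 1 | Vitreq contact lens |
| 2 | none |
| 5 | reusable yellow lens |
| 6, 7 | reusable yellow and green lenses |
| 8 | reusable green lens |

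Five of the eight endpoints name a reference. Endpoint 2 is worded as a comparison and does not.

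**Step 2. Do other sections supply it?** The synopsis and section 2.1 give a set: the reusable lenses and the contact lens. The device table in section 5 lists a reusable 128D (yellow) and a reusable 60D (green) lens, but no reusable ultra wide-angle lens, so there is no like-for-like counterpart. The yellow lens is the natural candidate, because it is the existing wide-angle lens and section 1.2 uses it for the distance comparison. No section assigns it to endpoint 2.

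**Step 3. Can the absolute half be shown?** The only figure in the plan is the sample size: 2 × 60 = 120, which agrees with the stated total. No fogging rate is given, so the rates below are assumptions. If each eye fogs independently with probability p, the chance of no fogging in n eyes is (1 − p)^n. With n = 120:

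| Assumed p | Calculation | Chance of 0 of 120 |
|---|---|---|
| 1% | 0.99^120 | 30% |
| 2% | 0.98^120 | 9% |
| 5% | 0.95^120 | 0.2% |

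If no eye does fog, the exact two-sided 95% upper bound for the true rate is 1 − 0.025^(1/n):

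- n = 120: 1 − 0.025^(1/120) = 3.0%
- n = 60 (one arm): 1 − 0.025^(1/60) = 6.0%

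A perfect result therefore remains compatible with fogging in about 3 eyes in 100. Without a stated threshold, the absolute claim cannot be demonstrated.

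**Step 4. Do less and no more differ in practice?** As an illustration, take fogging as yes or no, compare within the eye by an exact two-sided McNemar test at 5% in 120 eyes, and assume that the two lenses fog independently within an eye. The chance of concluding that the ultra wide-angle lens fogs less is:

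| Assumed rate, reference lens | Assumed rate, ultra wide-angle lens | Chance of concluding less |
|---|---|---|
| 10% | 5% | 23% |
| 20% | 10% | 51% |
| 30% | 15% | 76% |
| 30% | 10% | 97% |
| 20% | 20% | 1.7% |
| 20% | 30% | about 0% |

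A lens that truly fogs no more than its reference (fifth row) would almost never be shown to fog less. The choice between the two claims therefore matters.

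**The case against.** The strongest reply is that this is a wording gap with an obvious answer. The study compares present lenses with new ones, section 1.2 measures this lens against the yellow lens, and the group expectation there is set against the reusable lens. A sensible reader would pick the reusable yellow lens. That is fair, and it is why the fix is cheap. The text still does not say so, and the set of comparators also contains the green lens and the contact lens.

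Three stronger readings are tempting, and the documents do not support them.

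- A reader might infer that the plan expects this lens to fog more, so that the endpoint runs against its own rationale. Section 1.2 says only that it may. What it lists as expected is no more, or minimum, condensation, and section 2.1 refers to better resistance to fogging. The sections are inconsistent; they do not predict more fogging.
- A reader might infer that the reference will be chosen after the results are known. Section 7.2.4 has the final statistical plan agreed before data lock and before any analysis. Because the surgeon records the outcomes knowing which lens was used, a choice after results have been recorded is possible, but it is not certain. The content of the case report form (Appendix 4) is not reproduced in the text available here and may define the fogging item.
- A reader might infer that one fogged eye fails the endpoint. The comparative alternative after the slash prevents that. The probabilities in step 3 apply to the absolute half only.

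It is also fair to say that replacing less with no more would change the investigator's claim. That choice belongs to the investigator; the requirement is only that one claim be stated.

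**Conclusion.** The point holds in this form: endpoint 2 lacks a reference lens, mixes an absolute with a comparative claim, and rests on a rationale that gives three different directions. The plan should be changed, because this is a primary endpoint and a reference lens not graded during surgery cannot be added afterwards.

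The absolute half cannot be demonstrated with 120 eyes. The upper bound of 3.0% after 0 of 120 needs no assumed fogging rate, only independent eyes. The 30%, 9% and 0.2% figures rest on assumed rates of 1%, 2% and 5%. The comparative half can be tested once a reference is named, but no power can be attributed to the plan, because it states no rates; the figures in step 4 are illustrations that also assume independence of the two lenses within an eye.

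**What to change.** Before the first surgery:

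1. Name the reusable 128D yellow lens as the reference for endpoint 2.
2. Grade fogging of the ultra wide-angle and yellow lenses in the same eye, using the fogging item that endpoint 5 already needs. Endpoint 5 does not say in which arm it is determined, so state that the yellow lens is graded in both.
3. Analyse the within-eye paired difference with a 95% CI over both arms. For count data section 7.2.1 names only the Pearson chi-squared test, which does not use the pairing, so a paired method has to be added if fogging is recorded as yes or no.
4. State one comparative claim. The investigator chooses less or not more; if not more, fix the margin in advance.
5. Remove the absolute claim as a success criterion and report the proportion of eyes without fogging descriptively with its CI.
6. Reconcile the two statements in section 1.2 with the wording of endpoint 2 in section 2.2.

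The cost is mostly wording. The practical downside is that the yellow lens must be available and graded alongside the ultra wide-angle lens in each eye. Section 1.1.3 describes two selectable lenses on the system, so where other lenses are compared in the same eye an exchange may be needed, and the estimate of about 30 seconds of extra surgery time in section 2.1 should be checked against that.
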